7.7. Storage and Analysis of Samples

Samples will be labelled in accordance with the Sponsor's usual requirements and relevant legislation (e.g., GDPR) and will be transported, stored, accessed and processed in accordance with national legislation relating to the use and storage of human tissue for research purposes and such activities shall at least meet the requirements as set out in the 2004 Human Tissue Act and 2006 Human Tissue (Scotland) Act. Once blood samples have been analysed for bone biomarkers they will be securely and appropriately disposed of in accordance with local site protocols. Once blood samples have been analysed, they will be disposed of in accordance with local site protocols. Analysis will take place in the Sponsor's clinical laboratories (Newcastle Laboratories) or via Newcastle Laboratories as part of a service level agreement with an external laboratory in compliance with the UK Data Protection Act 2018, the UK GDPR as amended on 01 January 2021 by regulations under the European Union (Withdrawal) Act 2018, and the 2004 Human Tissue Act.

7.8. End of Trial

The end of the trial is defined as the last 36-week follow-up visit (or the last follow up safety phone call) of the last participant to reach this point, or the date of the last data gathered from questionnaires, blood samples or MRI analysis, whichever is the later. The sponsor, CI, and TSC have the right to terminate the trial at any point for clinical or administrative reasons.

The end of the trial will be reported to the Sponsor, Research Ethics Committee (REC), Human Regulatory Authority (HRA) and NHS R&D Office(s) within 90 days, or 15 days if the study is terminated prematurely. It is the Cl's responsibility to ensure that any appropriate follow-up is arranged for all participants; this will be delegated to the site PIs.

A final report will be provided to the Sponsor, REC, MHRA and Funder within their specified time frames. A lay summary will be made available to all participants via the trial's varying media.

Subject to further successful funding a substantial amendment may be submitted to HRA, Ethics, R&D and MHRA to cover longer term follow of participants beyond the stated end point above.

7.9. Post-trial care

At 36 weeks participants will return to routine NHS standard clinical care with the referrer/treating clinician. If the patient wishes to continue TAU, this can occur at the discretion of the referrer/treating clinician but suggested taper off regimens will also be provided for these clinicians.

Continuation of any injectable therapy will be reliant on the local NHS formulary funding arrangements for these interventions and may not be possible following completion of the trial until any positive outcomes from the trial that support changes in local formularies take effect which may be some time. This is pre-specified in the consent and PIS for the study. No provision for continuation of trial medication will be made by the trial team or Sponsor.

8. TRIAL MEDICATION

8.1. Name and Description of IMPs

Four IMPs are used within three arms in this trial: oral amitriptyline hydrochloride, oral gabapentin, lidocaine hydrochloride injection B.P. 2%, Botulinum toxin type A injections. Amitriptyline and gabapentin are within the same arm as 'treatment as usual' (TAU). The other two injectable IMPs form individual and separate arms. Participants will be randomised using three stratification variables (7.1.5) 1:1:1 to one of the three arms: TAU, Botulinum toxin type A injections, or Lidocaine 2% injections.

Amitriptyline 10mg and 25mg tablets (any brand) for oral administration will be used.

Gabapentin 100mg, 300mg, and 400mg capsules (any brand, unless lactose is flagged as a problem to the patient in which case a lactose free capsule will be selected using NHS SPS preferred method through the EMC database to exclude Lactose as an excipient) for oral administration will be used.

Botulinum toxin A will be provided as a 100 Allergan unit vial of $Botox^{TM}$ (AbbVie Ltd, Maidenhead, UK) for reconstitution with 0.9% Normal saline and injection intramuscularly.

Lidocaine 2% solution (any brand) will be provided as a 2ml ampoule for injection intramuscularly.

The following SmPCs will be used for the trial:

Medication	SmPC
Gabapentin	Neurontin 100mg Hard Capsules
Amitriptyline	Amitriptyline 10mg Film-Coated Tablets
Lidocaine 2%	Lidocaine Hydrochloride Injection BP 2% w/v
Botox	BOTOX 100 Allergan Units Powder for solution for injection

Serious adverse reactions (SARs) that are thought to have a causal relationship with the IMP must be assessed for expectedness against the current, approved version of the RSI. Market authorisation holders may update the SmPC over the trial's duration. The CI/Sponsor/NCTU will monitor and review any changes to SmPCs, considering the impact on the trial and then revise any relevant documentation as required.

8.2. Drug Storage and Supply

All IMPs will be sourced by each individual site's local pharmacy via standard NHS routes and kept in accordance with UK legislation, local protocols, and the products' Summary of Product Characteristics (SmPC).

Amitriptyline (any brand) requires no special storage conditions.

Gabapentin (any brand) needs to be stored at <25 degrees Celsius and as a Schedule 3 controlled drug (CD no Register Exempt Safe Custody) in the UK, it must comply with current UK controlled drugs regulations.

Botox should be stored at 2-8 degrees Celsius in a refrigerator prior to constitution. Any Botox that has not been reconstituted and is surplus to requirements should be disposed of in line with local trust policies/protocols. Any reconstituted Botox that is left over after patient administration should be disposed of in line with local trust policies/protocols.

Lidocaine 2% needs to be stored away from light at <25 degrees Celsius. Any residual lidocaine should be disposed of in line with local trust clinical policies/protocols.

Returned and unused injectable IMP will be disposed of at site in accordance with local trust requirements. Vials or similar containment vessels for the injectable IMPs, including packaging, will not be returned to pharmacy. Records of IMP disposal must be kept in line with GCP requirements.

8.3. Preparation and Labelling of IMPs

The use of the four IMPs is routine within clinical practice for TMD and therefore pose no greater risk than routine clinical care. The IMPs in use are licensed, marketed products with one (Botox) requiring reconstitution. There is therefore no requirement for accountability, segregated storage, temperature monitoring or labelling compliant with annex 13 for this trial. All IMPs will be provided in the standard approved manufacturer's packing with their labelling and patient information leaflets. For oral amitriptyline and gabapentin as prescribed medications for self-administration the pharmacy applied label will comply with current UK regulations.

8.4. Dosage Schedule & Modifications

This is a pragmatic trial in respect of the use of the oral medications in the TAU arm. Broad guidance is given but clinicians can follow their routine clinical practice subject to ceiling and safety thresholds. It is therefore important that dosages and tapering regimen are fully documented in the eCRF.

Trial investigators must therefore pay careful attention to the relevant SmPCs for guidance regarding posology, contraindications, special warnings and precautions for use, interactions, fertility, pregnancy and lactation, and effects on ability to drive and operate machinery for use of each of the

four IMPs which includes appropriate dose reductions as appropriate due to age or renal function. SmPCs will be provided to each site prior to the site commencing recruitment and the relevant sections are 4.2-4.7.

[figure not shown]
In TAU amitriptyline is recommended as first-line if not trialled previously unless the participant is epileptic, or ≥60 years of age, or is on another serotonergic agent for example SNRI, SSRI, Triptan. In the first two incidences (epilepsy diagnosis or age), due to amitriptyline's adverse effect profile further discussion will occur with patient over which drug, they would prefer to trial in the TAU arm (amitriptyline or gabapentin). Those patients meeting an exclusion criterion for amitriptyline (see exclusion criteria 19-24 which includes use of other serotonergic agents) will be offered gabapentin instead. Amitriptyline and gabapentin dosing titration and regimen are determined by clinician's usual practice but should lie within or below/slower than NICE's stated parameters (NICE, 2021):

- Starting doses: 10mg amitriptyline once daily in the evening; either 100mg or 300mg of gabapentin once daily, then twice daily on day 2, and then three times daily on day 3.
- Titration interval: quickest allowed for gabapentin and amitriptyline is 1 week and slowest is 4 weeks.
- Titration increments: 10mg increments of amitriptyline. 100-300mg increments for gabapentin which could be applied to all the three times daily regimen or one- or two of the three-times daily intakes.
- Ceiling doses: 75mg amitriptyline, 3600mg gabapentin
- Duration of therapy: trial amitriptyline or gabapentin for at least 8-12 weeks with a minimum of 2 weeks at the most effective or tolerable dose
- Issues of tolerability will be discussed with the patient and recorded in the CRF with a possible step back to the previous dose to see if a longer duration at this dose is either more effective or allows upward titration due to accommodation of any adverse effects.
- Discontinuation: unless an emergency the *quickest* allowed discontinuation would be spread over 4 weeks or slower for amitriptyline and gabapentin in similar increments or smaller than upwards titration dose steps. Much slower tapering off over a number of months of either drug is permissible and often required/desirable.

The same standardised sites and doses for the injectable IMPs will be used for both injectable IMPs and all patients. These are based on data suggesting they are the sites with the widest safety margins for adverse effects from the injectable IMPs (Hu et al., 2010; Lee et al., 2017; Peng and Peng, 2018). Bilateral masseter and temporalis will be injected for all patients.

The sites for injection are detailed in figures 1 and 2. All injections should be provided bilaterally using a 27-30 gauge 12.7-13mm detachable needle with a graduated 1.0ml syringe following skin cleaning in accordance with local aseptic non touch technique policy. The needle ideally can be replaced after one side has been injected. Figure 3 demonstrates the injection sites without penetration of skin in a volunteer.

Figure 1 Masseter – a) Anatomical structures; b) Positioning of injection sites with anatomy; c) Positioning of injection sites without anatomy

[figure not shown]

a) Safest zones in masseter are estimated using four anatomical lines – superior line, ear lobe to commissure; inferior line, mandibular angle to chin along inferior border of mandible; anterior line, anterior border of masseter; posterior line, posterior border of masseter. These four lines create a parallelogram. The boundaries of the safe zone within the parallelogram lie 1cm from each of the lines (area of darker blue shading). They therefore stay away from the facial artery and vein and parotid gland as well as the major branches of the facial nerve

b) The three injection sites are indicated (red dots) and should be a minimum of 1cm apart and at least 1cm from the edges of the parallelogram. The inferior two sites should be injected by angling the needle tip away from the facial artery/vein and parotid at the anterior and posterior boundaries respectively and the needle should contact bone before withdrawing ~2-3mm and aspirating before administering the Botox or 2% Lidocaine. The superior site may not touch bone but if at ~12mm depth with a negative aspiration the Botox or 2% Lidocaine can be administered.

Image redrawn from (Peng and Peng, 2018)

[figure not shown]
Figure 2 Temporalis – a) Anatomical structures and identifying zones; b) Safest zones for injection; c) Positioning of injection sites

- a) Dotted curved line indicates the most superior extension of temporalis tendon; vessels are superficial temporal artery and vein. Four anatomical lines and grid in yellow are created for safest zones for injection described under (b)
- b) Safest zones in temporalis (green shaded boxes) are estimated using four anatomical lines (in yellow) superior line parallel to most superiorly palpable part of Temporalis; inferior line runs along tragal canthal line; anterior line is the posterior border of the zygomatic-frontal process; posterior line runs parallel to most posterior part of the convexity of the pinna. These four lines then create a square which is divided into an equally spaced 3x3 grid (in yellow) with the three safest zones within this grid for deposition of Botox or 2% Lidocaine demonstrated in green whereas the higher risk zones are demonstrated in red.
- c) The three injection sites are indicated (red dots) and should be a minimum of 1cm apart. All sites should ideally be **within the hair** (unless bald) to avoid visible anterior temporal fossa atrophy and inadvertently weakening frontalis and causing brow changes. Bone should be contacted in all sites before withdrawing ~2-5mm and aspirating before administering the Botox or 2% Lidocaine.

Image adapted and redrawn from (Lee et al., 2017)

Figure 3 Injection sites on a volunteer: a) all three sites simultaneously demonstrated within safest zones of masseter (would be injected individually); b-d) three sites demonstrated individually (anterior to posterior [left to right]) within safest zones of temporalis on a volunteer.

100 units of Botox should be reconstituted with 2mls of 0.9% normal saline once the participant attends and confirms is going ahead with treatment. The vial's diaphragm should be wiped prior to reconstitution with a cleaning wipe. Brand of cleaning wipe will be determined by local aseptic non touch technique policy. Dosages per injection site are then:

- Masseter 10 units (0.2mls) per injection site = total 30 units per muscle
- Temporalis 5 units (0.1mls) per injection site = total 15 units per muscle
- Total dose per patient = 90 units. Maximum ceiling dose 100 units.

2mls of 2% Lidocaine will be used in same sites and volumes as for Botox. Volumes of Lidocaine per injection site are then:

- Masseter 0.2mls (4mg) per injection site = total 0.6ml per muscle
- Temporalis 0.1mls (2mg) per injection site = total 0.3ml per muscle
- Total dose per patient = 36mg. Maximum ceiling dose 40mg.

The cycles of injections provided will follow the schedule of events in section 7.4.10: day 0; week 12 +/- 7 days; week 24 +/- 7 days.

Doses selected for the injectable IMPs are based on the best quality evidence currently available for BTX and local anaesthetic injection therapy in M-TMD balancing risk of adverse effects against effectiveness (Al-Moraissi et al., 2020; Chan et al., 2016; De la Torre Canales et al., 2020; Machado et al., 2018; Nouged et al., 2019). The doses chosen provide the maximum chance of effectiveness and lowest chance of adverse effects, with the ceiling doses positioned well within the safety margin for the drug (\leq 25% of the total possible dose in one administration) and at the lowest end of the range of doses given to these muscles (Thambar et al., 2020). The BTX dosing scheduling is contemporary with current practice in the UK (Anwar et al., 2022) and consistent with the NICE recommendations for injectable (intramuscular) treatment of another trigeminally mediated pain (chronic migraine) which completes after the third cycle if no therapeutic effect is felt by the patient (Bendtsen et al., 2018; NICE, 2012). The Lidocaine dosing schedule is within the parameters within the published literature at the conservative end of repeated injections and mirrors the BTX scheduling given Lidocaine is an active comparator within the trial (Al-Moraissi et al., 2020; De la Torre Canales et al., 2020; Nouged et al., 2019).

Please note participants can elect to stop receiving any of the IMPs and can continue within the trial (details in section 7.6).

8.5. Known Drug Reactions and Interactions

The Summary of Product Characteristics (SmPC) for the four trial IMPs will be referenced for the safety information for sites in this trial. Specifically, the investigators should be aware of the following potential interactions:

Amitriptyline is contraindicated with monoamine oxidase inhibitors (exclusion criteria) and severe interactions have been observed with sympathomimetic agents, bupropion, cinacalcet, clozapine, dronedarone, fluoxetine, lithium, ozanimod, paroxetine and terbinafine.

Gabapentin requires caution around co-prescription with any other medication known to exert respiratory depression or CNS depression and if being prescribed in older adults, and any patient who may have compromised respiratory, renal, or neurological function (MHRA 2017)

Participants receiving lidocaine should be clinically observed as per usual practice.

No interactions of clinical significance have been noted for gabapentin or Botox.

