6.2. Exclusion Criteria

A documented diagnosis, or the patient reports any, of the following:

- Current use of any of the trial interventions or has used any within the last 12 weeks*#.
 Patients can continue any other treatment modality they currently find helpful for their TMD subject to no absolute contraindications to its use alongside the interventions under investigation.
- 2. Any other subtype of TMD that is the primary cause of familiar pain detected on clinical examination; familiar pain is pain provoked by clinical exam or testing/movement of a structure that matches the patient's primary complaint e.g., for M-TMD familiar pain is provoked from examination or use of the muscles of mastication. Patients can have other forms of (painful) TMD comorbid with M-TMD, but these should not be the primary cause of familiar pain determined by DC/TMD derived diagnostic procedures.
- 3. Enrolled in another interventional research trial which could affect the outcome of this trial.
- 4. People who are pregnant, planning pregnancy, or breast-feeding during the time of the trial participation*.
- 5. Current or planned acupuncture within trial period or 3 months prior to trial period*.
- 6. Formal diagnosis of lactose intolerance or lactose allergy and unable / unwilling to receive oral capsules of lactose free gabapentin if randomised to the treatment as usual arm**.
- 7. Fibromyalgia
- 8. Neuropathic pain
- 9. Coagulopathy
- 10. Uncontrolled hyperthyroidism
- 11. Renal failure
- 12. Severe liver disease
- 13. Connective tissue disorders e.g. Ehlers-Danlos syndrome, Epidermolysis bullosa, Marfan syndrome, Osteogenesis imperfecta, Rheumatoid arthritis, Poly/dermatomyositis, Scleroderma, Sjogren's syndrome, Systemic lupus erythematosus, Vasculitis
- 14. Any (previous) substance use disorder
- 15. Concerns from the research or clinical team over patient safety due to psychosocial distress, previous or current mental health illness*
- 16. Taking any of the following groups of medications:
 - a. Aminoglycoside antibiotics
 - b. Anticholinesterases
 - c. Non-depolarising and depolarising muscle relaxants
 - d. Opiates other than codeine. If taking codeine (including co-codamol), please see footnote†
 - e. Monoamine oxidase inhibitors (MAOIs)
- 17. Allergy or intolerance to any trial intervention, or any contraindication as per each IMP SmPC
- 18. For the MRI sub study group:

- a. cardiac pacemaker, defibrillator or pacing wires.

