 - For any other formulation of codeine, if its dosage ≥ 30mg in a singular ingestion or more frequently than every 4 hours, a principal investigator led risk assessment should be conducted and recorded, to ensure that if the patient was to receive Treatment As Usual there are no other are no other sedative drugs e.g. benzodiazepines, z-drugs etc or other comorbidities that might place the patient at greater risk of respiratory depression or challenges e.g. diminished respiratory function or sleep apnoea. If there are any concerns, the patient will not be eligible for the trial
 - No other type of opiate, other than codeine dosing as referred to above, is allowed on trial entry

^{*}If the chronology of events allows, the potentially eligible patient can be booked to be rescreened for a place on the trial at an appropriate point in the future.

All codeine use, at trial entry and during the trial, must be recorded in medications section of CRF

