8.6. Concomitant Medications

Simple analgesia (Ibuprofen, Aspirin, Paracetamol, co-codamol) are permitted and will be recorded via the database at screening (Visit 1) and throughout the trial. Use of prescribed opiates for a non TMD event should be reported in the database and a risk assessment considered if the participants are receiving Treatment As Usual, to determine if there are any risks associated with contraindicated medications. All repeat medications will also be recorded in the clinical notes and database.

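### Section 8.5 denies any clinically significant gabapentin interaction just after warning about one

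*Protocol*

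**What the plan says.** Section 8.5 of the protocol names the SmPCs of the four trial drugs as the source of safety information for sites. It then introduces a list with "Specifically, the investigators should be aware of the following potential interactions". The gabapentin entry reads "Gabapentin requires caution around co-prescription with any other medication known to exert respiratory depression or CNS depression", and extends the caution to older adults and to patients with impaired respiratory, renal or neurological function. After a line on observing participants given lidocaine, the section ends with "No interactions of clinical significance have been noted for gabapentin or Botox".

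Three other places bear on the same risk:

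- **Section 6.2, exclusion 16.** Five drug groups (a to e) are excluded. Item d covers opiates other than codeine. Benzodiazepines and z-drugs are in none of the five.
- **Section 6.2, codeine footnote.** For codeine products other than co-codamol, at or above a stated dose or frequency, the principal investigator must lead a risk assessment. In case the patient is allocated to TAU, it must look for "sedative drugs e.g. benzodiazepines, z-drugs etc or other comorbidities that might place the patient at greater risk of respiratory depression". Any concern makes the patient ineligible.
- **Section 8.6.** Prescribed opiates taken during the trial for a non-TMD reason are to be reported, and "a risk assessment considered if the participants are receiving Treatment As Usual".

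**The concern.** The last sentence of 8.5 tells the prescriber the opposite of what the gabapentin entry has just said. This is working safety guidance on an investigational product, in the section a clinician would open to check a co-prescription.

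Gabapentin will be used routinely in the TAU arm. It is offered to anyone who meets an exclusion for amitriptyline, including users of SSRIs, SNRIs or triptans. It is also the TAU drug for people who cannot take lactose or who already take pregabalin or nortriptyline for other reasons, and it is an option for those aged 60 or over or with epilepsy. Doses may reach 3600 mg daily, titrated by usual practice, and GPs may do the prescribing.

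What is at stake is a sedative combination passing unremarked because the closing sentence appears to clear gabapentin. No estimate or error rate is involved.

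**Working it through.** No arithmetic decides this point, so the check sets the texts side by side.

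**1. Within section 8.5.**

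| Statement | Content | Position |
|---|---|---|
| A | Caution when gabapentin is co-prescribed with respiratory or CNS depressants | In the list of potential interactions |
| B | No clinically significant interaction noted for gabapentin or Botox | Final sentence |

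A concerns giving gabapentin together with other drugs, and the section itself classes it as a potential interaction. B is unqualified: it does not limit itself to interactions beyond those listed. A and B therefore conflict for gabapentin. Nothing in 8.5 conflicts with B for Botox.

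**2. Can another section reconcile them?** No. The codeine footnote in 6.2 is concerned with factors that "might place the patient at greater risk of respiratory depression" if the patient receives TAU, and 8.6 raises a risk assessment for opiates in TAU participants. Both side with A. Neither names gabapentin as the interacting drug, and exclusion 16d applies to all three arms, so these are indirect support. The direct contradiction is between A and B.

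**3. Who is left relying on 8.5?**

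- *Opiates other than codeine at entry:* excluded by 16d, whatever 8.5 says.
- *Codeine other than co-codamol, at or above the footnote's threshold:* risk assessment under the footnote.
- *Prescribed opiates during the trial for a non-TMD reason:* 8.6 applies.
- *Co-codamol within the limits (single doses up to 30 mg codeine, at most four times daily):* accepted by the footnote without a risk assessment, and listed in 8.6 as permitted simple analgesia. The dose limit is the control.
- *A benzodiazepine or z-drug without codeine:* not in exclusion 16 and outside the footnote. Section 8.6 has no risk-assessment trigger for it. The remaining guidance is the general instruction in 8.4 to follow the SmPCs, and statement A, which B undercuts.

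**4. Upper bound on the number exposed.** With 663 participants randomised 1:1:1, the TAU arm has 663/3 = 221. Those affected are the subset who take gabapentin and also take a CNS depressant not caught by the codeine and opiate rules. The protocol gives neither proportion, so 221 is only a ceiling. Because amitriptyline is recommended first-line, the true figure will be well below it.

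**The case against.** The strongest reply is that nothing in practice depends on the closing sentence. Section 8.4 says "Trial investigators must therefore pay careful attention to the relevant SmPCs for guidance regarding posology", and goes on to cover warnings and interactions; the SmPCs go to every site before recruitment. Exclusion 17 bars anyone with an SmPC contraindication to a trial drug. Medications are recorded at screening and reviewed at weeks 12, 24 and 36, and the investigator reviews the TAU prescription at weeks 12 and 24. The caution is specific and sits in the same short section, so a reader would probably take the last sentence to mean that there is nothing further to add. On that view this is a wording slip.

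Most of this stands as a limit on the consequences. A careful investigator is not left without guidance, and no eligibility rule, dose rule or reporting trigger depends on the sentence.

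It does not rescue the sentence itself. Reading it as none beyond those above supplies a qualifier that the text lacks. Section 8.4 points to a warning held in another document and does not state it. Recording a co-medication does not tell the prescriber that the combination needs care.

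**Conclusion.** The concern holds. The closing sentence of 8.5 is false for gabapentin on the section's own terms. It is best described as an internal inconsistency in safety guidance, with limited practical effect, and it should be corrected.

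The group most dependent on the wording is gabapentin users taking a benzodiazepine or z-drug without codeine. Their number is unknown, with a ceiling of 221. The conclusion rests only on the protocol text. It assumes nothing about what the gabapentin SmPC says on these drugs, which cannot be checked here. Sample size, power, type I error and the planned analyses are untouched.

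**What to change.** In the last sentence of 8.5, remove gabapentin so that the statement covers Botox alone. Alternatively, reword it to say that no other clinically significant interactions are noted beyond the respiratory and CNS depressants already listed. Keep the caution as it stands, and add a cross-reference from it to the codeine footnote in 6.2 and to 8.6.

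The cost is two deleted words and a cross-reference at the next amendment, with no change to data collection or analysis.
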